SBRT	Stereotactic Body Radiation Therapy
SHIM	Sexual Health Inventory Men
SIB	Simultaneous integrated boost
STAMPEDE	Radiotherapy to the primary tumour for newly diagnosed, metastatic prostate cancer
SUSAR	Suspected Unexpected Serious Adverse Reaction
TRUS	Transrectal Ultrasound
UAP	Unanticipated Problem
WCMC	Weill Cornell Medical College

Summary of changes for version 5.0 dated 26JUL2023

Sections	Change	Rationale
Principal Investigator section	Changing Principal investigator from [name] to [name]	Changing Principal investigator from [name] to [name], since [name] will no longer be at WCM.
No changes to the Informed consent since the study is closed to accrual and only in follow up.		

Summary of changes for version 4.0 dated 03FEB2022

Sections	Change	Rationale
Primary Objective	Revising the toxicity measurement timeframe stated in the primary objective from 30 days to 3-6 months post treatment.	Revising the toxicity measurement timeframe stated in the primary objective from 30 days to 3-6 months post treatment and keep it consistent with the study calendar.
Personnel changes	Adding [name] to the protocol cover page.	Updating personnel and contact information. Admin amendment approved on 16NOV2021.
No changes to the Informed consent		

Summary of changes for version 3.0 dated 05OCT2021

Sections	Change	Rationale
Principal Investigator section	Changing Principal investigator from [name] to [name]	Changing Principal investigator from [name] to [name]
Personnel changes	Removed [name] as Nurse practitioner and [name] as study coordinator, Added [name]. Updated contact details for personnel.	Change of personnel and contact information.
Informed consent changes		
Principal Investigator section	Changing Principal investigator from [name] to [name]	Changing Principal investigator from [name] to [name]

Summary of changes for version 2.0 dated 24JAN2020.

1. **Inclusion Criteria:** Must have metastatic prostate cancer proven on biopsy or imaging
2. **Exclusion Criteria:** Removing criteria # 4 - Evidence of disease progression on bone scan, MR and/or CT
3. Revised accrual ceiling to 25 patients as stated in the IRB application
4. Adding [name] as data manager to the protocol to keep it consistent with the IRB personnel list.
5. Updating QOL – AUA to I-PSS
6. Study Calendar – clarifying that blood/stool collection is optional at all time points as stated in the informed consent.

Informed consent changes:

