1. The protocol version date is incorrect - changing the footer of the informed consent.
2. Making study calendar consistent with the protocol.

Document History

Document Name	Version number	Version Date
Amendment 4	5.0	26JUL2023
Amendment 3	4.0	03FEB2022
Amendment 2	3.0	05OCT2021
Amendment 1	2.0	24JAN2020
Initial Protocol	1.0	23JUL2019

Protocol Summary

PRAGMA (Prostate Radio Ablation Guided by Magnetic resonance imaging Acquisition) in metastatic prostate cancer

IRB Protocol #: 19-04020263

Short Title:	MRI-guided prostate SBRT for metastatic prostate cancer
Principal Investigator:	[name]
Sample Size:	N = 20
Accrual Ceiling:	This study plans to enroll a total of 25 patients
Study Population:	Patients with metastatic prostate cancer
Accrual Period:	2 years
Study Design:	Single-arm study for safety

Study Intervention Description:

MR-guided Prostate SBRT:

Prostate SBRT has become a standard of care for the treatment of localized prostate cancer. Radiation is delivered to the prostate and seminal vesicles in 5 treatment sessions (fractions). Doses ranging from 35-45 Gy in 5 fractions have demonstrated good outcomes with acceptable toxicity when planning is delivered appropriately.

There is emerging evidence that patients with *non*-localized prostate cancer also derive benefit from radiation (RT) to the primary tumor. The STAMPEDE multiarm British trial recently reported that patients with low burden metastatic prostate cancer have an overall survival benefit from prostate RT. Doses of radiation used in the STAMPEDE trial were either 36 Gy in 6 fractions, or 55 Gy in 20 fractions.

The MRidian ViewRay offers delivery of prostate SBRT with real-time MR guidance, which provides superior soft-tissue differentiation with excellent visualization of the prostate. This ViewRay platform offers the ideal setting for this study, that aims at precisely delivering prostate SBRT with a simultaneous integrated boost (when indicated) to visible nodules.

In this study, we hope to demonstrate the safety of using 36.25 Gy in 5 fractions, plus a simultaneous integrated boost (when indicated), in patients with metastatic prostate cancer.

Hypothesis: Patients with metastatic prostate cancer can undergo MRI-guided prostate SBRT without significant adverse events, similar to what has been reported for patients with localized prostate cancer.

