2.8 Rationale for Correlative Studies Background: Microbiome and blood sample collection

Patients accrued to the study will donate a stool specimen and a blood sample both before and after radiation, to study their changes in the microbiome and circulating immune correlates during and after radiotherapy, and at 3-6 month follow up.

Preliminary results from our ongoing study “Effect of Radiotherapy Variables on Circulating Effectors of Immnue Response and Local Microbiome” PI: [name], IRB Protocol #: 1708018471 demonstrate depletion of circulating lymphocytes in prostate cancer patients undergoing protracted standard radiation compared to 5-fraction SBRT (which is the regimen we will use on this study) (results submitted to ASTRO). We will study this phenomenon further in patients undergoing SBRT on this study. We have also found a temporary increase in neutrophil:lymphocyte ratio (NLR) during radiation to the prostate in our dataset of patients; patients enrolled on this protocol will also have assessment of NLR at baseline, after RT and at 3-month follow up.

The host microbiome is an emerging topic of investigation, with growing evidence that commensal microbiota impacts anti-tumor immune response, and sensitivity to systemic therapies and immunotherapy. Commensal bacteria outnumber human cells by at least 10-fold, colonizing host mucosal surfaces and playing critical roles in metabolism, defense against pathogens, and crosstalk between the environment and immune system. Preclinical studies suggest that microbiota impact the immune system through a number of mechanisms, including possible modulation of myeloid-derived cells; stimulation of T helper cells, and enhancement of memory T-cell response. Dysbiosis, or shifts in microbial composition, may modulate response to cancer therapy. We hypothesize that the underlying microbial community composition will be impacted by administration of radiation to the prostate. Our preliminary data in mice suggests fluctuations in composition, abundance and diversity after local tumor-directed radiation. We hope to explore this further in patients who are undergoing SBRT by collecting microbiome samples at baseline, upon completion of RT, and at follow up.

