5 STUDY PROCEDURES

	Pre-Study	Fx 1	Fx2	Fx 3	Fx 4	Fx 5*	Post-RT Visits (3-6 months, 9- 12 months s/p RT)
Informed consent	X						
Demographics	X						
PSA	X						X
Acute/Late Toxicity Assessment (CTCAE)	X					X	X
EPIC-26, I-PSS	X						X
Imaging: Planning CT/MR;	X						
Blood draw and microbiome sample	X					X	X**

** no blood draw at 9-12 months.

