9 CORRELATIVE/SPECIAL STUDIES

9.1 Correlative Study: Blood draws for immune correlates and microbiome collection

Patients will provide blood draw prior to, at the completion of radiation and at 3-6 months post treatment follow up. They will also be providing a stool sample for microbiome analysis at baseline, end of completion and 3-6 month follow up (last stool sample is optional). This is a correlative study.

Blood Sample Collection and Procedure

Blood samples (40-ml) will be collected in heparinized “Green Top” tubes (for PBMC and plasma isolation) and processed within 4 h of sample receipt. The PBMC will be isolated using a 1.077 g/ml Ficoll layer to enrich the leukocytes and remove the dead cells and any red cells, and cryopreserved in 10% DMSO, 90% human AB serum at 10×10^6

cells/vial and stored in liquid nitrogen for batch analysis. Plasma will also be aliquoted and stored at -80°C for batch analysis. We anticipate analyses of T cell subsets and neutrophil/lymphocyte ratios, as well as cytokine measurement and proliferation analyses (all markers of peripheral immune correlates to assess status over time).

Microbiome collection

Collection of Specimen(s): Patients will be provided with a stool collection container and be instructed on providing a specimen appropriately, which can be done from home or in the clinic.

Handling of Specimens(s): Samples received will be promptly frozen at 20 degrees C, and transferred within the next week to a -80 degree freezer or liquid nitrogen for long-term storage. DNA extractions and 16sRNA analysis will be performed once all samples are collected.

The microbial DNA will be isolated and used to provide DNA sequence information. We will perform taxonomic characterization of bacteria (using 16S rRNA). Prokaryotic diversity will be screened using massively parallel DNA sequencing, exploiting a multiplexing technique to generate 16S rRNA sequence tags, followed by analyses (statistical, clustering, and phylogenetic) to estimate the distribution of phylotypes, differential abundance, and the relative contributions between phylotypes and community dissimilarities to the overall diversity in individuals.

We will examine whether there are metagenome sequence content changes during radiation treatment, and study whether differences in gene content indicate differences in functional pathways between the normal and irradiated microbiome using pathway analysis.

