12.1.3 Correlative Study Objectives

Microbiome and labs will be collected for exploratory analyses to see how radiation impacts the host microbiome and peripheral immune correlates found in blood.

12.2 *Sample Size/Accrual Rate*

We plan to accrue 20 patients over 2 years, or about 4-6 patients every 6 months.

12.3 *Analysis of Primary and Secondary Endpoints*

Primary Endpoint:

The treatment will be deemed safe if the grade 4+ likely radiation treatment related GI/GU adverse event rate is less than 10% within 3-6 months of the end of treatment. The proportion of patients that experience a >grade 3 GU/GU adverse event will be determined with a binomial

point estimate and corresponding exact 95% binomial confidence interval. If the lower bound of the interval is below 10%, the treatment will be considered safe.

Secondary Endpoints:

QOL measures at baseline and at follow up (3-6 months post treatment start, and 9-12 months) will be summarized numerically and graphically using mean (sd), median (interquartile range), or count (percent) as appropriate, and 95% confidence intervals estimated where possible. The QOL value will be plotted over time with a line for each patient and a smoothed curve superimposed on the plot. Changes in scoring from pre- to post-treatment will also be determined. EPIC-26 overall scores as well as domain summary scores (urinary incontinence, urinary irritative/obstructive, bowel, sexual, hormonal) and individual item responses will be evaluated. Similarly, overall score as well as individual item responses will be assessed for the I-PSS survey.

Toxicity will be assessed using CTCAE 5.0 criteria at 3-6 months and 9-12 months.

These analyses will be descriptive.

Correlative study endpoints:

Microbiome

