Plasma samples will be collected at three time points: before radiation, following completion, and 3-6 months after completion. We hope to understand the impact of radiation on the distribution and frequency of peripheral immune mediators at these time points. To this effect, NLR will be numerically and graphically summarized in several ways. The average ratio at each time will be estimated, as well as average changes from baseline, and individual trajectories will be plotted in “spaghetti plots.” Parallel summaries will be presented dichotomizing N/L ratio at 4%, counting the proportion of patients above this threshold at each time point.

Several markers beyond N/L ratio are of interest in order to thoroughly characterize changes throughout radiation treatment, including continuous (e.g. T cell panel and TREG panel, IL-7, IL-15, IL-6, IL-10, IL-17, IL-2 cytokines), and categorical (e.g. proliferative ability) measures. These will be summarized and analyzed in an exploratory manner in parallel methods to N/L ratio, if funding is secured for these analyses.

13 Data and Safety Monitoring Plan (DSMP)

The WCMC Data and Safety Monitoring Committee (DSMC) is the central monitoring board for this study.

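### Section 12.3 splits the unitless neutrophil:lymphocyte ratio at 4%; applied literally (0.04), this one exploratory summary would sit near 100% at all three time points and be practically insensitive to change

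*Combined protocol and SAP*

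**What the plan says.** The CBC paragraph of Section 12.3 describes NLR in several ways at three time points: before radiation, after completion, and 3-6 months later. The continuous summaries come first: "The average ratio at each time will be estimated, as well as average changes from baseline", with individual trajectories plotted as well. The dichotomized summary follows: "Parallel summaries will be presented dichotomizing N/L ratio at 4%, counting the proportion of patients above this threshold at each time point".

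Other sections name NLR but give neither a unit nor a threshold. Section 9.1 says "We anticipate analyses of T cell subsets and neutrophil/lymphocyte ratios". Section 2.8 says "patients enrolled on this protocol will also have assessment of NLR at baseline, after RT and at 3-month follow up". Hypothesis 3 in Section 1 and the correlative objectives in Section 1.3 also treat it as a plain ratio.

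The footnote to the study calendar in Section 5, "no blood draw at 9-12 months", agrees with three blood samples per patient. Section 12.2 gives the planned size ("We plan to accrue 20 patients over 2 years") and the Protocol Summary gives the ceiling ("This study plans to enroll a total of 25 patients"). The summary of changes for version 2.0 describes one edit as "clarifying that blood/stool collection is optional at all time points as stated in the informed consent", so the number of samples may be smaller.

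**The concern.** A percent sign is attached to the cut-off of a quantity that has no percent scale. Two ways of rescuing it do not work:

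- If neutrophils and lymphocytes are both recorded as percentages of white cells, the percent signs cancel in the ratio.
- The figure cannot be a percent change from baseline, because the rule is applied at every time point, including baseline.

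That leaves the literal value of 0.04, which is so low that nearly every patient would be above it at every visit.

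The protocol expects NLR to move. Hypothesis 3 anticipates a decline that recovers by follow-up, while Section 2.8 reports a temporary increase in the department's own data. A proportion held near its ceiling informs neither expectation. An analyst who sees the problem would have to apply a cut that the plan does not state, possibly after seeing the data.

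**Working it through.** The document gives no derivation of the cut, so there is no figure to reproduce. The check is a unit conversion followed by an illustration.

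**Inputs from the document.** Cut 4% (Section 12.3); three time points (Sections 5 and 12.3); 20 patients planned (Section 12.2); ceiling of 25 (Protocol Summary).

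**Assumed inputs.** NLR is log-normal with median m from 1 to 6 and log-SD s up to 1.0. A median of 0.5 is added for a visit at which NLR has halved from 1. None of these values is in the document.

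**Step 1, units.** 4% = 0.04 = 1/25. As a share of neutrophils plus lymphocytes combined, this is 0.04/1.04 = 3.8%.

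**Step 2, share below the cut.** P(below) = Φ((ln 0.04 − ln m)/s). The cut lies under every assumed median, so P(below) is largest at the smallest m and the largest s.

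| Median m | log-SD s | z | P(below 0.04) | Share above |
|---|---|---|---|---|
| 2 | 1.0 | −3.912 | 4.58 × 10⁻⁵ | over 99.99% |
| 1 | 1.0 | −3.219 | 6.43 × 10⁻⁴ | 99.94% |
| 0.5 | 1.0 | −2.526 | 5.77 × 10⁻³ | 99.42% |
| 1 | 0.7 | −4.598 | 2.13 × 10⁻⁶ | over 99.99% |
| 0.5 | 0.7 | −3.608 | 1.54 × 10⁻⁴ | 99.98% |

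**Step 3, expected values below the cut over the whole study, s = 1.0, no missing samples.**
- Median 1 at all three visits: 20 × 3 × 6.43 × 10⁻⁴ = 0.039 of 60 values; 25 × 3 × 6.43 × 10⁻⁴ = 0.048 of 75.
- Median 1 at two visits and 0.5 at one: 20 × (2 × 6.43 × 10⁻⁴ + 5.77 × 10⁻³) = 0.14 of 60; the same sum × 25 = 0.18 of 75.

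**Step 4, response to change, 20 patients, starting from median 1 and s = 1.0.**
- NLR doubles: the expected count above goes from 19.987 to 20 × (1 − 4.58 × 10⁻⁵) = 19.999.
- NLR halves: it goes from 19.987 to 20 × (1 − 5.77 × 10⁻³) = 19.885, a change of 0.10 of a patient. At the ceiling of 25 it goes from 24.984 to 24.856, a change of 0.13.
- NLR halves with s = 0.7: the change is 20 × (1.54 × 10⁻⁴ − 2.13 × 10⁻⁶) = 0.003 of a patient.

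**Step 5, does the reading of the cut matter?** For illustration only, with a cut of 4 and s = 1.0, the expected share above is 24% at a median of 2 (4.9 of 20) and 66% at a median of 6 (13.1 of 20). With a cut of 0.04, both are essentially 100%.

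**The case against.** The strongest reply is that an analyst would read the figure as a ratio of 4 and ignore or query the percent sign, especially since the same paragraph speaks of an average ratio. On that view the defect is a mistyped unit, and the ceiling effect never occurs. This is plausible, and it is why the consequence here depends on literal application. It does not settle the matter, because no section restates the cut as 4 or gives a basis for it. A reader might infer that 4 was certainly meant; the document does not support that.

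A reader might also infer that the summary could not register any rise or fall at all. That goes too far. Values below 0.04 would be counted, and Step 4 shows a small movement when NLR halves. Practically insensitive is what the numbers support.

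It is also fair to say that every probability above rests on an assumed distribution. That stands, although the conclusion changes little over a wide range of medians and spreads.

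Finally, the summary is descriptive and belongs to an exploratory correlative study, and no test or decision uses the cut. That also stands, and it limits the severity. It also means that a clarification in the report could be enough.

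**Conclusion.** The point holds as a minor one. The stated cut does not fit the scale of the variable, and nothing else in the document corrects it. If 0.04 is applied, the proportion above the cut is about 100% at each of the three time points: at least 99.94% for medians of 1 to 6, and about 99.4% at a median of 0.5, assuming a log-normal NLR with log-SD up to 1.0. In the least favourable case examined, a halving of NLR moves the expected count by about a tenth of one patient in 20.

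A reader might go on to infer that the NLR analysis as a whole is compromised. The document does not support that. The average ratio, the changes from baseline and the individual trajectories do not use the cut, and no primary or secondary endpoint depends on it.

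**What to change.** Replace 4% in the CBC paragraph of Section 12.3 with the intended cut on the ratio scale, preferably with a short statement of its basis. Do this in a dated amendment before NLR is analysed. The document does not say whether that analysis has been done. If it has, disclose in the report which cut was used and when it was set. If the sponsor cannot settle on a cut, drop the dichotomized summary and rely on the continuous summaries already planned.

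The cost is one line in an amendment or one sentence in the report. No new data are needed; by the version 5.0 summary of changes, the study is closed to accrual and in follow-up.

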13.1 Monitoring plan

This study will be conducted in accordance with the guidelines in the 2001 NCI approved data Safety and Monitoring plan for the WCMC Cancer Institute Monitoring will occur on a yearly basis from the date the first patient is enrolled. Reports to the Data Safety and Monitoring Committee will include the following information: accruals, targets, responses, adverse events and evidence of reporting to appropriate review committees. The WCMC Data and Safety Monitoring Board (DSMB) will review the IRB approved protocol, the data and safety monitoring plan and any stopping guidelines during protocol initiation. During the course of the study, the DSMB will review cumulative study data twice a year to evaluate safety, efficacy, study conduct, and scientific validity and integrity of the trial. The WCMC DSMB may also convene as needed if stopping criteria are met or other safety issues arise that the Principal Investigator and/or IRB would like the WCMC DSMB to address.

13.2 Stopping rules

If more than 2 patients experience a grade 4 likely radiation treatment related adverse event, the study will suspend accrual and the study team will evaluate the adverse events to determine whether they were at least possibly related to treatment. A decision will be made with approval of the DSMB to either modify the protocol or to terminate the trial due to an unacceptable adverse event rate.

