12.1.1 Primary Objectives

Safety of this approach will be determined by assessing acute GI/GU toxicity (CTCAE 5). The treatment will be deemed safe if no more than 3 patients experience a grade 4 likely radiation treatment related GI/GU (or higher) adverse event within 3-6 months from the end of treatment.

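### The accrual-suspension rule in section 13.2 counts grade 4 events only, while the safety criterion in 12.1.1 and 12.3 counts grade 4 or higher, so a grade 5 event adds nothing to the suspension count as written

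*Combined protocol and SAP*

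**What the plan says.** Section 13.2 gives the trigger: "If more than 2 patients experience a grade 4 likely radiation treatment related adverse event, the study will suspend accrual". After suspension the study team assesses the events, and "A decision will be made with approval of the DSMB to either modify the protocol or to terminate the trial". The rule names one grade. It has no organ-system restriction and no time window.

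The safety criterion is worded differently. Section 12.1.1 calls the treatment safe if "no more than 3 patients experience a grade 4 likely radiation treatment related GI/GU (or higher) adverse event" within the window after treatment. Section 12.3 states it as a rate: "The treatment will be deemed safe if the grade 4+ likely radiation treatment related GI/GU adverse event rate is less than 10" percent. Sections 1.1, 2.7 and 10 likewise use a threshold above grade 3, which takes in grade 5.

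Two other routes bear on serious events. Section 13.1 has the DSMB review cumulative data twice a year and lets it meet as needed. Sections 7.3 to 7.4 send serious adverse events, including deaths, to the IRB.

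The planned size is 20 ("We plan to accrue 20 patients over 2 years, or about 4-6 patients every 6 months"), with a ceiling of 25. The version 5.0 summary of changes records that the study is closed to accrual and in follow-up.

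**The concern.** The suspension rule and the safety criterion should recognise the same severity, or the plan should say why they do not. Here the difference runs the wrong way for a monitoring rule: the end-of-study criterion includes the most severe grade and the rule that protects patients during accrual does not. A treatment-related death would count against the treatment in the final analysis, yet add nothing to the count that suspends enrolment.

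The two rules also differ in scope. Section 13.2 covers any radiation-related adverse event at any time; 12.1.1 and 12.3 cover GI/GU events in a window. The DSMB's count and the primary-endpoint count can therefore differ in either direction, and the plan does not say whether that is deliberate.

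**Working it through.** The documents give no operating characteristics for the stopping rule, so there is no stated figure to reproduce. The check compares the wording and then counts.

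**1. What each rule counts**

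| | 13.2 (suspension) | 12.1.1 and 12.3 (safety criterion) |
|---|---|---|
| Grade | 4 | 4 or higher |
| Event type | any adverse event | GI/GU only |
| Attribution | likely related to radiation | likely related to radiation |
| Time window | none | 3-6 months from end of treatment |
| Limit | suspend at 3 patients | 12.1.1: not safe at 4 patients; 12.3: rate must be below 10% |

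**2. Counting examples.** Each patient is classed by highest grade. All events are likely radiation-related and within the window.

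| Patients with events | Count under 13.2 as written | Count under 12.1.1 | Suspended? |
|---|---|---|---|
| 3 with grade 4 GI/GU | 3 | 3 | yes |
| 2 with grade 4, 1 with grade 5, all GI/GU | 2 | 3 | no |
| 3 with grade 5 GI/GU | 0 | 3 | no |
| 2 with grade 4, 2 with grade 5, all GI/GU | 2 | 4 | no, although 12.1.1 fails |
| 3 with grade 4, none GI/GU | 3 | 0 | yes |

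The second to fourth rows show the grade gap. In the fourth, the treatment fails its own safety count without accrual having been suspended. The last row shows the scope difference working in the other direction.

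**3. Scale, under assumptions.** The documents give no grade 4 or grade 5 rate. Suppose a patient has a grade 4 or higher event with probability p, and a share f of those events is grade 5. The literal count over 20 patients is then binomial with probability q = p(1 - f), and

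P(3 or more of 20) = 1 - [(1-q)^20 + 20q(1-q)^19 + 190q²(1-q)^18].

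With p = 20% (assumed, well above the plan's 10% limit):

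- f = 0: q = 20%, P = 79.4%. This is also the result for any f if grade 5 is counted.
- f = 10%: q = 18%, P = 1 - (0.0189 + 0.0829 + 0.1730) = 72.5%.
- f = 25%: q = 15%, P = 59.5%.
- f = 50%: q = 10%, P = 32.3%.

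The loss depends wholly on f. It is zero if no grade 5 event occurs, and the larger shares are shown only to mark the range.

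**4. Whether another provision closes the gap.** The twice-yearly DSMB review is by calendar, the ad hoc meeting is discretionary, and the serious-event route leads to the IRB. None sets a number of events at which accrual stops.

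**The case against.** The best defence is that this is a drafting slip. Every statement of the safety criterion reaches grade 5, so a sensible DSMB would read 13.2 the same way, and many patients with a fatal event would have passed through grade 4 first. A treatment-related death would also go to the IRB and could prompt an ad hoc DSMB meeting. This stands as a reason to expect little practical harm. It does not remove the need to reconcile the text, because a rule that suspends accrual should not rest on inference.

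The wider scope of 13.2 is also defensible: monitoring all radiation-related events beside a GI/GU endpoint is a legitimate and more protective choice. What is missing is only a statement that it is intended.

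A reader might go further and infer that, because the trigger has no denominator, two events in the first three patients would escape review and the trigger should be derived by exact binomial from the 10% limit. The documents do not support this.

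- Review is not absent. The DSMB meets twice a year, and planned accrual is 4-6 patients per 6 months, so a scheduled review falls about every 4-6 patients.
- The trigger is not detached from the limit. With 20 patients, 2/20 = 10% and 3/20 = 15%, so three is the first count above 10% of planned accrual. It also comes one patient before the 12.1.1 count fails.
- An exact-binomial trigger would mostly loosen monitoring. At an assumed 5% per look against a true 10% rate, the threshold is 2 events at 2-3 patients, 3 at 4-8, 4 at 9-14 and 5 at 15-20, so it is looser than the present rule from patient 9 onward. With looks after every patient and outcomes known at once, the probability of suspension by patient 20 at a true 20% rate falls from 79.4% to 45.6%, and mean patients treated rises from 13.6 to 15.4.

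**Conclusion.** The concern holds for the grade wording. As written, 13.2 gives grade 5 events no weight, while 12.1.1 and 12.3 count them, and no other provision suspends accrual at a set count. This rests on the text alone; the probabilities above rest on assumed rates and shares and only indicate scale.

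The likely practical effect is small. The plan expects almost no severe acute toxicity, the omission is probably unintended, and accrual is closed, so no patient's exposure can now change. What remains at stake is whether a suspension should have occurred and how that is reported.

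The scope difference is a point to clarify, not an error. The lack of a denominator is not upheld as a defect. Which grade threshold is clinically right is for the sponsor and is not judged here.

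**What to change.** - Reconcile the grade wording of 13.2 with 12.1.1 and 12.3, so that the treatment of grade 5 events under the suspension rule is explicit.
- State in 13.2 whether covering all adverse events, with no time window, is intended to be wider than the GI/GU criterion.
- Apply the reconciled count to all accrued patients, and report whether suspension of accrual and DSMB review should have been triggered and whether they were.

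The cost is a phrase and a sentence in the protocol, plus a recount from adverse event logs that the study already keeps. No new data and no change to the sample size are needed.
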